2.1. Rational: As many prostate cancer (PCa) cases diagnosed at early stage are indolent, PCa progression risk- stratification systems have been developed, based on biopsy characteristics, staging and PSA levels, and patients are classified into low- intermediate- and high-risk groups for treatment stratification. However, these systems are imperfect. Moreover, determining which curative treatment will be most effective for individual patients with localised PCa is challenging and remains a major obstacle in improving patient management and is recognised as an unmet clinical need. Cancer metastasis is the main cause of PCa death and determines the selection of therapeutic methods. Theoretically, localised PCa should be cured by radical prostatectomy (RP). However, more than half of apparently localised high-risk PCa cases treated by RP reoccur, indicating the presence of undetectable micro-metastasis at the time of surgery. These particular patients require additional treatment, usually with radiotherapy and systemic hormone therapy. The major challenge in managing aggressive localised PCa is differentiating truly localised PCa from those with micro-metastatic disease, which cannot be cured by RP. Pelvic lymph node dissection for high-risk localised disease is the current diagnostic test for assessing spread of disease but is invasive and performed during surgery. A test is required which can be performed before surgery to distinguish patients suitable for RP from those who would benefit from more extensive systemic treatment and radiotherapy. No current imaging test has the resolution to detect micro-metastases that may consist of just a few viable PCa cells. Circulating tumour cells (CTCs), the seeds of cancer metastasis, can occur at a very early stage of cancer development. We hypothesise that detection of CTCs provides an accurate indicator of cancer micro-metastasis and CTC gene expression may predict the potential of future metastasis development. We have established a promising CTC analysis method, by which we have detected CTCs in all patients with metastatic PCa and for the first time have demonstrated the value of using CTC analysis in predicting **clinically significant** post-biopsy **clinically significant** PCa outcome in pre-biopsy patients. Our CTC results may reflect the existence of micro-metastasis and predict PCa progression risk better than the current imperfect risk-stratification systems. Therefore, a prospective study with

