	
To provide a preliminary assessment of the prognostic value of CTC data (positivity and gene expression) in predicting post-RP PCa metastasis development, overall survival and cancer specific survival.
 
To provide evidence and data which can be used to design a future clinical trial of a CTC- based intervention to be used to guide therapeutic choice in the management of high-risk localised PCa.
 
To evaluate the longer-term prognostic value of CTC detection and CTC gene expression for metastases and cancer-specific survival.
 
Primary endpoint
 
The primary outcome is post-RP treatment failure during the first 4.5 years of follow up from start of recruitment.
 
Post-RP treatment failure is defined as a PSA $\geq 0.2\text{mg/ml}$ at the routine PSA test 3 months after RP (commonly called 'failure to nadir') and remaining at this level or further increase afterwards without further treatment, or imaging detected appearance of cancer lesions.
 
Cancer lesions detected by imaging without a PSA rise might include neuroendocrine PCa and lesions detected by PSAM-PET. This combined post-RP treatment failure primary endpoint will maximally capture all the clinically significant cancer appearance events.
 
Secondary endpoints
 
BCR during the first 4.5 years of follow up: PSA $\geq 0.2\text{ng/ml}$ at any time post-RP and remaining at this level or further increase afterwards without further treatment.
 
Metastasis (any location)-free survival during the first 4.5 years of follow up. Only 5% of subjects with distant metastasis event (based on traditional imaging technologies) within this time frame (4-6).
 
Metastasis (any location)-free survival at 10 years follow up. to confirm that metastatic event rates have increased among the positives, i.e. a declining rate of "false positives".
 
Deaths from any cause during the first 4.5 years of follow up
 
Overall survival at 10 years of follow up.
 
Prostate cancer specific deaths during the first 4.5 years of follow up. Expected to be 2% or less based on previous studies in the post RP context.
 
Prostate cancer specific survival at 10 years of follow up. Our hypothesis is that most if not all of the patients dying of PCa will be in the CTC positive group.

Target sample size	294

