Each patient will be allocated a unique ID and will be used by the lab research team. This unique ID will be recorded in the tissue bank database for future correlation analysis of the CTC results with clinical follow-up data. Sample processing will be performed in tissue culture hood in the designated lab. The whole blood sample will be processed within 4hrs for CTC analysis after collection. Standard Operating Procedure (SOP) (C-ProMeta-1) that is generated describing sample process and analyses need to be followed. There will be fewer patients for the post-RP than the pre-surgery blood collection based on patient exclusion criteria after RP.

Based on the sample size calculation 200 patients will be recruited for both pre- and post-surgery blood sample collections for CTC analysis, which are expected to be achieved within the first two years of the project.

Patient informed consent (including the permission to conduct remote longer-term follow-up) and blood sample collection will be performed by the CRF or the clinical care team.

All patients will have a PSA test at 3 months after their RP during a routine follow-up at UCLH. A PSA ≥ 0.2 will be recorded as a treatment failure event and PSMA-PET scans will be performed as standard clinical care at the study hospitals to detect small PCa lesions. After 3 months, patients are referred back to their original referring centres. Patients with negative PSA results at three months will be followed up by telephone or online app by the study CRF in order to ascertain whether subsequent PSA tests are positive (PSA ≥ 0.2), indicating BCR, metastasis occurs as detected by cancer imaging including PSMA-PET scan or if they have received salvage treatment with hormones/radiotherapy. In addition, details of long term follow up, such as post-operative PSA results and record of adjuvant therapies, will be sourced from patients' hospital electronic medical records, or requested from their local GP or health centre. All patients will be followed-up until the end of the project for metastasis progression as detected by imaging, PCa-specific death and death from any causes. In addition to data collected within the 5-year funded period, we plan to conduct remote longer-term follow up with fully informed consent from patients at point of enrolment, including:

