- **MRI score:** Multi-parametric MRI Likert scale 1-5 where >3 indicates aggressive cancer.
- **BCR:** PSA $\geq 0.2\text{ng/ml}$ at any time post-RP and remaining at this level or further increase afterwards without further treatment (see Table 4 for endpoint definitions)
- **Post-RP treatment failure:** (see Table 4 for endpoint definitions)

2). Sample size

The study hypothesis is that the presence of CTCs has close to 100% sensitivity and specificity for micro-metastasis, and thus RP treatment failure. Due to the long-term nature of recurrence events, there will be a proof of principle part to this study which occurs within the funded study timeframe of 5 years, and an intention to collect and analyse relevant longer-term events at 10 years (see section 4 for objectives and endpoints). The primary endpoint is **post-RP treatment failure**, the majority of which will be due to BCR. Despite the long-term nature of events of interest, it will be possible to provide a timely estimate of sensitivity, since of those who do have an observable BCR event, most if not all are expected to have a positive CTC result. Thus, consistent with previous work, this study estimates predicting post-RP cancer events with 95% sensitivity. During the first 4.5 years of follow up, the hypothesised prevalence of BCR events to be at least 40%.

In order to confirm an expected sensitivity of 95% within 5% precision either side of a 95% confidence interval (CI) in a sample with an underlying prevalence of 40%, requires at least 73 events, that is at least 183 recruited individuals. Inflate this by 8.5% to a target recruitment of 200 to ensure suitability of samples and measurable outcomes.

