will be reported alongside the number of these participants with a positive by CTC result, and positive combined CTC result. Metastases-free, PCa-specific and overall survival will be reported during the 5 years study time frame and it is intended to perform a later analysis at 10 years of follow up. Preliminary investigation of the prognostic value of pre-surgery CTC data in terms of predicting survival outcomes will be investigated using Cox regression, with hazard ratios reported with associated 95% CIs. CTC data will be explored alongside other pre-surgery risk factors such as plasma PSA using multivariate analysis. Recurrence events and follow up CTC results will be reported and compared over time. The above analyses will be applied to the CTC gene panel. The gene panel will also be correlated with the pre- and post- RP CTC number changes and cancer progression events.

CTC results will be presented for the whole cohort who provided analysable blood samples and stratified by those included in the above analyses, and those excluded due to reasons such as a positive surgery margin, other evidence of locally remaining disease, and who subsequently have adjuvant ADT or radiotherapy.

8. Ethics

The study is a spin out project of the parent project authorised under RLTB ethics, where the main research tissue bank approval provided by the London City & East Research Ethics Committee.

9. Data handling, storage and record keeping- to describe who and how the data will be handled, which data nodes will be used, where it will be stored and security of the data

The CRF (funded by QMUL, but with contract at UCLH) will be part of the study management group and will act as the contact point between UCLH and QMUL. Under the MTA and data sharing agreement (DSA) between the two institutions and with patient consent, the CRF will collect blood samples during pre-surgery operation and after the surgery during the first PSA follow-up visit at UCLH.

The following clinical data will be collected for each patient by the CRF:

- Histology reports
- Clinical stage
- Prostate Specific Antigen (PAS) (pre- and post-surgery)
- Imaging (MRI, PSMA-PET/CT and bone scan)
- Results and record of adjuvant therapies
- Treatment date and method for post-surgery cancer recurrence

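### The protocol gives incompatible rules for post-RP treatment failure: Table 1 needs a persistent untreated PSA (or a lesion on imaging), while Section 6 counts a single PSA ≥0.2

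*Protocol*

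**What the plan says.** Section 3, Table 1 (Primary endpoint) defines post-RP treatment failure by two routes. The PSA route is a value of at least 0.2 at the routine 3-month test, qualified by "and remaining at this level or further increase afterwards without further treatment, or imaging detected appearance of cancer lesions". The last words of that quote are the second route, imaging, which is sufficient whatever the PSA. The threshold in this sentence is in mg/ml.

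BCR, in Table 1 (Secondary endpoints) and in Section 7 (Statistical considerations, Definitions), has the threshold in ng/ml and may occur "at any time post-RP and remaining at this level or further increase afterwards without further treatment".

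Section 6 has a different recording rule for the 3-month test: "A PSA ≥ 0.2 will be recorded as a treatment failure event and PSMA-PET scans will be performed as standard clinical care". Men below the threshold at 3 months are then contacted "in order to ascertain whether subsequent PSA tests are positive", and a positive result is taken to indicate BCR. Neither statement asks for persistence or for absence of treatment.

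The statistical methodology row of Table 1, the matching paragraph in Section 7 and the Method of analysis all describe failure more simply, as BCR or progression on imaging. The Definitions in Section 7 refer to a Table 4 for endpoint definitions. That table is not in the text at hand.

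**The concern.** The no-treatment condition and expected care pull against each other. Of men who recur after surgery, Section 2.1 says: "These particular patients require additional treatment, usually with radiotherapy and systemic hormone therapy". Section 6 asks about salvage hormones or radiotherapy during follow-up, and Section 9 lists "Treatment date and method for post-surgery cancer recurrence" among the data to collect. Yet salvage treatment is not a component of either failure rule. Once a man is treated, his later PSA values can no longer show persistence without treatment.

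The primary analysis is the sensitivity of pre-surgery CTCs for treatment failure. The outcome rule sets its denominator and also determines specificity and both predictive values. If the early treated failures are coded as non-failures, the CTC-positive men among them count as false positives. The Sample size section calls specificity important because a positive test might in future deny a man curative surgery.

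**Working it through.** **Classification under each rule.** All of these men are without a lesion on imaging, except in the last row.

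| Man | Table 1, primary endpoint | Section 6 |
|---|---|---|
| PSA ≥0.2 at 3 months, salvage treatment before a second PSA | PSA route cannot be met | Failure |
| PSA ≥0.2 at 3 months, untreated, later falls below 0.2 | Not a failure | Failure |
| PSA ≥0.2 at 3 months, untreated, persists | Failure | Failure |
| PSA ≥0.2 at 3 months, lesion on imaging | Failure | Failure |

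A further mismatch lies outside Section 6. A man below 0.2 at 3 months who has a sustained untreated rise later, with no lesion, has BCR. He is therefore a failure under the methodology row of Table 1 and under Section 7. He does not meet the PSA route of the primary endpoint in Table 1, which is tied to the 3-month test.

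**The plan's own figures (Section 7, Sample size).** Inputs: expected sensitivity 95%, precision ±5 points, 95% confidence, prevalence 40%, inflation 8.5%.

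- Events: 1.96² × 0.95 × 0.05 / 0.05² = 72.99, so 73.
- Men: 73 / 0.40 = 182.5, so 183.
- Inflated: 183 / (1 − 0.085) = 200.

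All three reproduce. At 200 men, expected failures are 200 × 0.40 = 80 and non-failures are 120.

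**Effect of reclassification.** Let f be the share of the 80 failures that move to non-failure under Table 1. The documents do not give f; 10% to 30% is assumed. It is also assumed that treated men stay in the analysis set and that 95% of those moved are CTC positive.

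- Events left: 80 × (1 − f), which is 72 at 10% and 56 at 30%. The count drops below 73 once f exceeds 1 − 73/80 = 8.75%.
- Sensitivity: 0.95 × 80 = 76 true positives at the start. (76 − 7.6)/72 = 95% and (76 − 22.8)/56 = 95%, so the expected value does not change.
- Half-width: 1.96 × √(0.95 × 0.05 / events), which is 4.8 points at 80 events, 5.0 at 72 and 5.7 at 56.
- Observed specificity, with true specificity s and m men moved: (120s + 0.05m) / (120 + m).

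| True s (assumed) | m = 8 (f = 10%) | m = 24 (f = 30%) |
|---|---|---|
| 100% | 120.4/128 = 94.1%, loss 5.9 points | 121.2/144 = 84.2%, loss 15.8 points |
| 70% | 84.4/128 = 65.9%, loss 4.1 points | 85.2/144 = 59.2%, loss 10.8 points |

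**The case against.** Several points on the other side stand, and they limit what can be claimed.

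- **Imaging narrows the group.** Section 6 has PSMA-PET done after a raised 3-month PSA, and a lesion is a failure under both rules. For the 3-month PSA rule, the conflict is confined to men without a lesion who are treated before a second PSA, and to untreated men whose single value falls.
- **A second PSA may be available.** The follow-up schedule in Section 6 shows PSA at 3 and then 12 months, but the same section also draws PSA results from hospital records and GPs. A reader might infer that persistence can usually not be observed. The documents do not show that: Section 2.1 gives no timing for further treatment.
- **Treated men may not be analysed at all.** The target of 200 in Section 5 counts men without later ADT (adjuvant ADT) or radiotherapy, and the end of the Method of analysis lists men with adjuvant ADT or radiotherapy among those excluded. On that reading the treated man never enters the two-by-two table and is not a false positive. This leaves his status unsettled in a further way; it does not reconcile the two rules.
- **Table 4 may settle the matter.** It could hold a single definition. Even so, the text of Table 1 and Section 6 would still disagree and need correction.
- **The unit is a slip.** A reader might make much of a factor of one million between mg/ml and ng/ml. BCR is given in ng/ml in the same table, so the intended unit is clear and the error adds little weight.

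**Conclusion.** The concern holds as a contradiction in the primary endpoint. Table 1 and Section 6 classify identifiable groups of men differently, and Table 1 also differs from Section 7 on whether a PSA failure after the 3-month test counts. Nothing in the available text resolves either difference.

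The consequence is conditional and mostly not about the primary estimate. A reader might infer that estimated sensitivity is biased. Under the assumptions above it stays at 95%, and only precision changes, from a half-width of 4.8 points to 5.0–5.7. It would shift only if the reclassified men differed from other failures in CTC positivity, on which the documents give no figure. The shortfall against 73 events is one event at 10% reclassified and 17 at 30%.

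The larger effect is on observed specificity. The loss of about 6–16 points applies only if true specificity is near 100%; at 70% it is about 4–11 points. The lower starting point matters because the Sample size section itself expects low observed specificity, and extra analyses for inflated false positives are already planned. All these figures assume that 10–30% of failures are affected and that treated men are analysed.

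**What to change.** State one definition of post-RP treatment failure. Use it in Table 1 (Primary endpoint and statistical methodology row), Section 6, Section 7 (methodology paragraph, Definitions, Method of analysis) and Table 4 if it exists. It should:

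- give the PSA threshold in ng/ml, as the BCR definition does;
- include BCR at any time within the 4.5-year window, so that the PSA route is not limited to the 3-month test;
- say how a PSA ≥0.2 followed by salvage treatment is classified, and how an untreated single value that later falls is classified.

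Counting a raised PSA followed by salvage treatment as a failure, dated at the first qualifying PSA, fits the aim stated in Table 1 of capturing as many clinically significant events as possible. This is a rule for coding outcomes and has no bearing on when or how anyone is treated.

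In the same edit, reconcile Section 5 and the end of the Method of analysis on whether men treated after surgery stay in the analysis set.

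The cost is protocol wording, since PSA results and treatment dates are already to be collected. The small downside is that a few failures will have no confirming PSA. The change should be made before outcomes are coded.

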Protocol for spin off research project- Circulating tumour cells as biomarkers to predict prostate cancer metastasis for treatment stratification of localised cancer

clinical outcome follow- up over a long period is required to confirm the value of this CTC analysis in determining micro- metastasis, i.e. predicting post-RP PSA failure and future metastasis development.

2.2. Aims:

- I. To establish the value of CTC positivity in predicting post-RP treatment failure, including BCR and new lesions detected by cancer imaging.
- II. To establish the value of a combined CTC test (including CTC enumeration and gene expression) in predicting post-RP treatment failure and the time of the development of BCR and new lesions detected by cancer imaging.
- III. To provide a preliminary assessment of the prognostic value of CTC data (positivity and gene expression) in predicting post-RP PCa metastasis development, overall survival and cancer specific survival and the generation of CTC data for future longer-term follow-up.
- IV. To provide evidence and data which can be used to design a future clinical trial of a CTC-based intervention to be used to guide therapeutic choice in the management of high-risk localised PCa.

3. Summary and synopsis

This study will require 10-year patient follow up for analyses of the primary and secondary endpoints to have statistically significant power. Nevertheless, extensive research activities will be mainly conducted in the first 5-years where research funding has been secured. After the first 5-years, further research activity will only include annual patient clinical follow-up, data collection and statistical analysis. A renewal application for further funding will be submitted by the end of the first 5-year funding period. The overall study set up is summarised in **Table 1**.

Table 1. Overall study summary.

Methodology	Single site, double-blinded, prospective, paired cohort study. Participating patients and clinicians involved in treatment or management will be blinded to the CTC results, to avoid influencing standard patient treatment, management, and progression outcomes after RP.

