The recruitment plan will be 200 patients in the first two years of the 5-year project to allow an approximate 3.5 to 4 year median follow up. Specificity is important considering the future circumstance of potentially denying patients curative surgery, if a CTC test indicates metastasis. A study size of 200 and 120 true negatives would give a 97.5% lower confidence limit on a specificity of 99% (1% false positive rate). However, it is anticipated the specificity will be low due to positive results for those who recur beyond the 5-year study. Assuming these events are due to micro-metastases at the time of surgery, observed sensitivity and specificity will be used, plus additional analyses assuming up to 20% of the events occur after the funded 5-year project⁴⁻¹¹ to estimate the real false positive and negative rates.

3). Method of analysis

Study flow and patient characteristics will be reported. Measures of accuracy will be presented with 95% confidence intervals (CIs). The primary analysis is the estimation of the sensitivity of the pre-surgery existence of CTCs for detection of RP treatment failure, i.e. BCR or progression detected by any imaging at the 4.5-year follow-up time point. Observed specificity, positive and negative prediction values will also be reported at 4.5 years of follow up, with a note to indicate that these estimates are subject to change given the long-term nature of recurrence events. Specificity will be presented over time and additional analysis accounting for artificial inflation of false positives based on increasing prevalence of events. BCR-free survival will be estimated and Kaplan-Meier curves presented.

The number of participants with recorded metastases, lymph node metastases, deaths from any cause and PCa deaths during the first 4.5 years of follow up

Protocol for spin off research project- Circulating tumour cells as biomarkers to predict prostate cancer metastasis for treatment stratification of localised cancer

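### The stated purpose of the 10-year metastasis endpoint, a rise in events among CTC positives, would be met almost surely by any marker and so cannot confirm the hypothesis

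*Protocol*

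**What the plan says.** Section 3, Table 1, Secondary endpoints, lists "Metastasis (any location)-free survival at 10 years follow up" and gives its purpose as "to confirm that metastatic event rates have increased among the positives". An i.e. clause then restates this as a declining rate of false positives, with that term in inverted commas. The sentence names no CTC-negative comparator, effect measure, threshold or expected 10-year rate.

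For the corresponding endpoint at 4.5 years the table gives an expected rate: "Only 5% of subjects with distant metastasis event (based on traditional imaging technologies) within this time frame".

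Other parts of the protocol bear on the same question:

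- Table 1 has a secondary objective on the longer-term prognostic value of CTCs for metastases. For 10-year cancer-specific survival it states a real contrast, namely that nearly all cancer deaths should fall in the CTC-positive group.
- Section 6 plans diagnostic accuracy and predictive value for metastases at 7.5 and 10 years.
- Section 7, Sample size, treats a specificity of 99% as the same thing as a 1% false positive rate. It also expects low observed specificity because some positives will recur only after the funded period.
- Section 7, Method of analysis, plans specificity over time with "additional analysis accounting for artificial inflation of false positives based on increasing prevalence of events". It also plans Cox regression with hazard ratios, described as preliminary, and a later analysis at 10 years.

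**The concern.** The protocol expects many CTC positives to be event-free at 4.5 years and explains this in advance: these men have micro-metastases that have not yet shown themselves. The 10-year follow-up is where that explanation can be tested. The test must be able to come out against it, and for that it has to ask whether late metastases occur more often in positives than in negatives.

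The sentence in Table 1 asks only whether events among positives have gone up. In a fixed group followed for longer, cumulative events stay level or rise. If a rise is reported as confirmation, a marker with no prognostic value would be confirmed too. The protocol itself says specificity matters because a positive test might one day be used to withhold curative surgery.

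**Working it through.** **The plan's own figure.** The only sample size calculation is for sensitivity at 4.5 years: 1.96² × 0.95 × 0.05 / 0.05² = 72.99, so 73 events; 73 / 0.40 = 182.5, so 183 men; 183 / (1 - 0.085) = 200. All three figures reproduce. No calculation is given for the 10-year metastasis endpoint.

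**Inputs.** N = 200 (section 7, Sample size) and 5% metastasis at 4.5 years (Table 1). The protocol gives neither the share of CTC positives nor the 10-year metastasis rate. I assume 40-60% positive and 10-20% metastasis, and work the middle case of 15% at 40% positive (80 positive, 120 negative).

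**Formulas.** With overall cumulative risk m, positive share p and risk ratio R (positive to negative), risk in negatives is m / (pR + 1 - p), and risk in positives is R times that.

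- 1 - PPV = event-free positives / all positives.
- 1 - specificity = event-free positives / all event-free men.

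**Uninformative marker (R = 1).** Events in positives go from 80 × 0.05 = 4 to 80 × 0.15 = 12, so 1 - PPV goes from 76/80 = 95% to 68/80 = 85%. In negatives, events go from 6 to 18 and the event-free share from 114/120 = 95% to 102/120 = 85%, the identical change. With 10% at 10 years, positives go from 4 to 8 events and 1 - PPV ends at 90%. By contrast, 1 - specificity is 76/190 = 40.0% at 4.5 years and 68/170 = 40.0% at 10 years.

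**Three markers, 40% positive, 5% rising to 15%:**

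| Marker | Events in positives | 1 - PPV | 1 - specificity |
|---|---|---|---|
| Uninformative (R = 1) | 4 to 12 | 95% to 85% | 40.0% to 40.0% |
| Wrong direction (R = 0.5) | 2.5 to 7.5 | 96.9% to 90.6% | 40.8% to 42.6% |
| Informative (R = 3) | 6.7 to 20 | 91.7% to 75.0% | 38.6% to 35.3% |

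Events in positives rise and 1 - PPV falls in every row. Only 1 - specificity tells the markers apart.

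**How sure is the rise?** Strictly, at least one new event among positives is needed. In the least favourable case (80 positives, 5% to 10%), the chance is 1 - 0.95^80 = 98.3% for the uninformative marker. For the wrong-direction marker, risk in positives goes from 3.125% to 6.25%, giving 1 - 0.96875^80 = 92.1%. A simulation of 20,000 runs per scenario gives 98.2% and 92.4% for these two cases. Over the whole assumed range the simulated results are:

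| Marker | Events in positives rise | 1 - specificity falls |
|---|---|---|
| Uninformative | 98.2-100% of runs | about 48-51% |
| Wrong direction | 92.4-100% | about 2-13% |
| Informative | 99.9-100% | about 95-100% |

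**What a contrast can deliver.** Late events number about 200 × (0.10 - 0.05) = 10 to 200 × (0.15 - 0.05) = 20. With 40% positive and a true hazard ratio of 3, the Schoenfeld approximation gives z = √(D × 0.4 × 0.6) × ln 3 - 1.96. For D = 10, z = 1.70 - 1.96 = -0.26, or about 40% power. For D = 20, z = 2.41 - 1.96 = 0.45, or about 67%.

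**The case against.** **The phrase is a rationale, not a decision rule.** It carries no test or threshold, and nothing says the hypothesis will be judged by it alone. That is fair. Still, it is the only purpose the protocol gives this endpoint, and it uses the language of confirmation.

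**The comparison is already planned.** A reader might infer from the sentence that the 10-year follow-up as a whole ignores CTC negatives and cannot count against the marker. The documents do not support this. Diagnostic accuracy at 10 years cannot be computed without negatives, and a hazard ratio for a binary CTC result compares positives with negatives. The plan for "additional analysis accounting for artificial inflation of false positives based on increasing prevalence of events" also shows that the authors know these measures move with time. This confines the flaw to the stated purpose of one endpoint. It does not repair that purpose, because the Cox work is called preliminary and nothing ties it to the claim to be confirmed.

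**The false positive rate may mean 1 - specificity.** Section 7 uses the term that way, and on that reading a decline does discriminate. So it would be too strong to say that every marker meets every reading of the sentence. But Table 1 equates the decline with a rise among positives, which is a different quantity, and the ambiguity needs settling. Likewise, if event rates meant events per person-year, a rise would not be automatic; the i.e. clause points to cumulative events instead.

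**The 5% is an imperfect starting value.** It refers to distant metastasis on traditional imaging, while the endpoint covers any location. The argument does not depend on the value. The protocol's allowance for up to 20% late events should not be carried over here, because it concerns treatment failure after the 5-year project, a different endpoint.

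**Conclusion.** The concern holds for the purpose and reading of 10-year metastasis-free survival as worded in Table 1. Read as cumulative events or 1 - PPV among positives, the stated finding would appear in at least 98% of simulated studies of an uninformative marker and at least 92% for a marker pointing the wrong way. It therefore gives no support to the idea that false positives at 4.5 years are true micro-metastases. These figures rest on assumed 40-60% positivity and 10-20% metastasis at 10 years; the direction of the argument needs neither. The rest of the 10-year plan can supply a valid comparison, and the primary endpoint and sample size are untouched.

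**What to change.** Replace the purpose in Table 1 with a contrast: metastasis-free survival to 10 years from surgery in CTC-positive versus CTC-negative men, as a hazard ratio or risk difference with 95% CI, together with time-dependent sensitivity and specificity. Define the false positive rate as 1 - specificity, as section 7 already does. Wherever a decline in false positives among positives is shown, show the matching change in CTC-negative men.

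A landmark analysis of late metastases may be added as supportive, provided the landmark is set for each man from surgery. The protocol's 4.5 years for the primary endpoint runs from the start of recruitment, which lasts 2 years, so it corresponds to roughly 2.5 to 4.5 years per man and cannot serve as a common landmark. Read this analysis by its estimate and interval. Requiring the interval to exclude no difference would be too strict for an analysis the protocol calls preliminary, given about 40-67% power at a hazard ratio of 3.

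The cost is a short edit to the endpoint table and no new data. The hypothesis attached to this endpoint could then fail, and with about 10-20 late events the estimate will be imprecise.
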